Participants will be excluded from the study if they have any of the following conditions:

1. Consumed any carnosine supplement of more than 6 grams per a week in the past 4 weeks (one month)
2. Current / ongoing treatment for substance abuse
3. Currently undergoing treatment or have conditions which may cause participant to be immunosuppressed
4. Diseases Affecting Peripheral Cell Count (i.e. Autoimmune Diseases – Hashimoto, Rheumatoid Arthritis, SLE, Rheumatoid Arthritis, Sjogren syndrome, Ankylosing Spondylitis, Takayasu arteritis, Kawasaki disease, Polyarteritis nodosa.)
5. Diseases Affecting Bone Marrow capacity
6. Diagnosis of any active cancer
7. Recent organ / kidney transplant or replacement (Active/Long-Term Medications)
8. Type 1 Diabetes Mellitus
9. Untreated thyroid disease
10. Untreated anemia
11. Current acute infections (Influenza, fever, etc.)
12. HIV positive status
13. Active/current Hepatitis HepA, HepB or HepC or in past 6 months
14. Pregnant / lactating or planning to

15. Prisoners / vulnerable populations
16. Other medical conditions that compromise completion of study
17. Unwilling to provide consent

Special Conditions of Exclusion (Screening or Main Study)

Candidates with the following conditions or history may be excluded:

1. **Local reactions:** diarrhea, stomach upset, tingling sensation in extremities, rash or itchiness, dry mouth, changes in appetite, feelings of tiredness, or vivid dreams.
2. **Systemic reactions:** fever, allergic reaction, anaphylaxis or any clinical untoward event that occurred with a known cause of taking dietary supplement.
3. **Abnormal laboratory results** which are deemed clinically significant with a known cause of taking dietary supplement.
4. **Pregnancy and breast-feeding:** Currently, there is not enough reliable information about the safety of taking carnosine supplement during pregnancy or breast-feeding. Hence, participants/candidates who are currently pregnant or breast-feeding or plan to be pregnant/breast-feeding during the study period will not be enrolled in the study.

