Participants that withdraw from the study before Follow-Up # 1 (Visit # 3) or do not complete Visit # 3 will be considered lost to follow-up. Existing data of these participants will be retained for further analysis.

Screen Failure

Candidates are considered screen failures when they meet one of the following criteria after signing consent:

1. Screening (Visit # 1) data reveals that the candidate is ineligible
OR

2. Candidate withdraws and does not complete Baseline Assessment (Visit # 2)

Discontinued

Participants are considered discontinued when they meet one or more of the following criteria:

1. Participant withdraws consent after being randomized
OR
2. Participant withdraws consent after completion of Baseline Assessment (Visit # 2)
OR
3. Participant fails to follow study supplement regimen
OR
4. Participant is unable to fulfill the inclusion/exclusion criteria during the study
OR
5. Participant refuses/is unable to provide critical data at follow-up visits as deemed necessary by the investigator
OR
6. Participant is withdrawn after randomization by investigator for reasons that may compromise completion of the study

Medical or Health Concerns

Participants will be instructed that in an event of an acute health concern (related or unrelated to the study supplement), they should immediately discontinue the study supplement and seek medical attention from a licensed healthcare provider. Participants will be provided with a study identification card. This card will contain the following information: name of the study, name of study institution, a statement to the effect of *“each capsule may contain 0.5 grams of L-Carnosine or 0.5 grams of cornstarch”*, method of contacting the study physician, and a method of contacting the study coordinator.

Participants may be able to re-start supplement regimen and continue the randomization after detailed discussions with the study physician. The study physician may seek advisement from the DSMB on these matters.

Compensation

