10. STUDY VISITS

Screening (Visit # 1)

The screening period extends from the date informed consent is signed until the day of randomization (Figure 3). The screening window will not exceed 180 days prior to randomization.

The following activities will be carried out at screening:

1. Informed Consent (for entire study)
2. Blood and or Urine sample collection
3. Demographic data
4. Contact information
5. Prepaid \$25 VISA gift card

Participants may be excluded from the study if any of the above screening data collection is not completed or meets an exclusion criterion during the screening period. Data gathered from screening (Visit # 1) will be used to identify whether the candidate meets the enrollment criteria for the main study and whether they are eligible to be randomized. Eligible candidates will be invited to participate in the main study and subsequently randomized in a double blind fashion.

Baseline Assessment (Visit # 2)

Baseline assessment will occur after eligible candidates have been identified via screening (Visit # 1) (Figure 4). Participants attending the baseline assessment (Visit # 2) will already be randomized into carnosine or placebo group. Participants will be provided with the study supplement during this visit and they will start their dietary supplement regimen (carnosine or placebo) immediately on the day of baseline assessment. The following activities will be carried out at Baseline Assessment:

1. Update Demographics and Contact Information
2. Questionnaire data on Medical History, Medications, Exposure to Environmental Pollution, Sleep, Diet, Exercise, Tobacco, and Women's Health
3. Blood sample collection (~3 tablespoons or ~45ml)
4. Urine sample collection (~2 tablespoons or ~30ml)
5. Arterial stiffness test (SphygmoCor)
6. Physical strength test (hand grip test, step test, calf raise test)
7. Provide 8 weeks of study dietary supplement capsules (carnosine or placebo)
8. Discuss schedule and related instructions related to taking the study dietary supplement
9. Prepaid \$50 VISA gift card

Participants may be excluded from the study if any of the above data collection is not completed or meets an exclusion criterion during this period.

Follow-Up # 1 (Visit # 3)

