Follow-Up # 1 will occur ~6 weeks after initiation of study supplement at the baseline assessment (Visit # 2) (Figure 5). Participants attending follow-up # 1 (Visit # 3) will have already been taking the study supplement for at least 5 weeks and no more than 7 weeks (6 weeks \pm 1 from Visit # 2). The following activities will be carried out at Follow-Up # 1:

1. Update Demographics and Contact Information
2. Update Questionnaire data on Medical History, Medications, and Women's Health
3. Questionnaire data Exposure to Environmental Pollution, Sleep, Diet, Exercise, Tobacco
4. Blood sample collection (~3 tablespoons or ~45ml)
5. Urine sample collection (~2 tablespoons or ~30ml)
6. Arterial stiffness test (SphygmoCor)
7. Physical strength test (hand grip test, step test, calf raise test)
8. Review the participant's dietary supplement regimen and any instances of deviation in regimen (missed or over consumption).
9. Provide 4 more weeks of study dietary supplement capsules (carnosine or placebo)
10. Discuss any side-effects which may have occurred or may arise from study supplement. Discuss any health changes during the study period.
11. Prepaid \$75 VISA gift card

Participants may be excluded from the study if any of the above data collection is not completed or meets an exclusion criterion during this period.

Follow-Up # 2 (Visit # 4)

Follow-Up # 2 will occur ~12 weeks after initiation of study supplement at the baseline assessment (Visit # 2) (Figure 6). Participants attending follow-up # 2 (Visit # 4) will have already been taking the study supplement for at least 10 weeks and no more than 12 weeks (11 weeks \pm 1 from Visit # 2). The following activities will be carried out at Follow-Up # 2:

1. Update Demographics and Contact Information

2. Update Questionnaire data on Medical History, Medications, and Women's Health
3. Questionnaire data Exposure to Environmental Pollution, Sleep, Diet, Exercise, Tobacco
4. Blood sample collection (~3 tablespoons or ~45ml)
5. Urine sample collection (~2 tablespoons or ~30ml)
6. Arterial stiffness test (SphygmoCor)
7. Physical strength test (hand grip test, step test, calf raise test)
8. Review the participant's dietary supplement regimen and any instances of deviation in regimen (missed or over consumption).
9. Discuss any side-effects which may have occurred or may arise from study supplement.
Discuss any health changes during the study period.
10. Prepaid \$100 VISA gift card

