Participants may be excluded from the study if any of the above data collection is not completed or meets an exclusion criterion during this period.

4 – 12 Month Safety Check (Visit # 5)

Although this interaction is termed as a “Visit”, it will not involve participants to physically be present. A follow-up email / phone call / mailed paper questionnaire will be conducted 4-12 months after the end of supplement intervention (Figure 7). This contact will focus on updating about any SAEs & medical / medication history changes since end of intervention:

1. Update Demographics and Contact Information
2. Questionnaire data on Medical / Medications History since end of intervention
3. Questionnaire data on adverse effects or SAEs since end of intervention.
4. No monetary compensation for this follow-up / check.

Participants will not be excluded from the study if any of the above data collection is not completed. Instead, they will be categorized as “lost to safety follow-up”.

Safety Evaluations during Study Visits

Adverse events will be assessed during Visit # 3 and Visit # 4 and through the 12 months after participants have stopped taking study supplement. The following will be documented in the adverse event reporting system:

1. **Local reactions:** diarrhea, stomach upset, tingling sensation in extremities, rash or itchiness, dry mouth, changes in appetite, feelings of tiredness, or vivid dreams.
2. **Systemic reactions:** fever, allergic reaction, anaphylaxis or any clinical untoward event that occurs within 30 days of beginning study supplement.
3. **Abnormal laboratory results** which are deemed clinically significant.
4. **Pregnancy and breast-feeding:** Currently, there is not enough reliable information about the safety of taking carnosine supplement during pregnancy or breast-feeding. Hence, participants/candidates who are currently pregnant or breast-feeding or plan to be pregnant/breast-feeding during the study period will be “discontinued” from the study.

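### Pregnancy is excluded because carnosine's safety in it is unknown, but no listed check can reveal a pregnancy the participant does not yet know about; a urine strip before dispensing at Visits 2 and 3 would detect some of these

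*Combined protocol and SAP*

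**What the plan says.** **The rule.** Section 9, Exclusion Criteria (All Visits), bars women who are "Pregnant / lactating or planning to". Section 10, Safety Evaluations during Study Visits, gives the reason, "there is not enough reliable information about the safety of taking carnosine supplement during pregnancy or breast-feeding", and says such participants will be discontinued. One discontinuation criterion in section 9 covers loss of eligibility: "Participant is unable to fulfill the inclusion/exclusion criteria during the study".

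**The checks.** Section 9, Prescreening, allows review of health information before consent. Section 10 lists a questionnaire at Visit 2 that includes women's health. At Visits 3 and 4 it lists "Update Questionnaire data on Medical History, Medications, and Women's Health" and a discussion of health changes. Section 8 describes the questionnaires as self-reported. No pregnancy test is listed in section 10, in the section 12 schedule, in Table 3 or in Appendices A and B. The stated use of the screening urine is the carnosine level.

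**Dispensing.** Randomisation precedes Visit 2. At Visit 2 the plan says to "Provide 8 weeks of study dietary supplement capsules (carnosine or placebo", and participants are told that "they will start their dietary supplement regimen (carnosine or placebo) immediately on the day of baseline assessment". At Visit 3, five to seven weeks later, it says to "Provide 4 more weeks of study dietary supplement capsules (carnosine or placebo". At both visits urine collection is listed ahead of dispensing (Visit 2 items 4 and 7; Visit 3 items 5 and 9).

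**The concern.** The sponsor has set a safety rule, and the listed procedures can enforce it only for a pregnancy the participant already knows about. The questionnaire comes before dispensing at Visits 2 and 3, so a known pregnancy can be picked up. A recent, unrecognised one cannot. Prescreening does not close the gap: it comes before consent, and screening alone may precede randomisation by up to 180 days.

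Women are eligible from age 22, and the listed criteria exclude those planning pregnancy without requiring contraception. A woman with an unrecognised pregnancy would therefore start capsules at Visit 2, or be re-supplied at Visit 3, with the plan followed exactly as written. What is at stake is avoidable exposure to a product whose safety in pregnancy the sponsor says is not established.

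**Working it through.** **Plan figures used.** The plan gives no figure on this point. It randomises 400: 240 / (1 − 0.40) = 400, which reproduces. The dose is 2 g/day (section 11, four 0.5 g capsules). Visit 3 falls at 5–7 weeks.

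**Assumptions, none from the documents.**
- n = 80–160 of the 400 could conceive.
- r = 1–10% yearly pregnancy rate.
- w = 2–4 weeks from conception to recognition.
- D = 1.5–2.5 weeks from conception until a strip can be positive.
- s = 0.90–0.99 sensitivity once detectable.
- Conceptions are spread evenly over time.

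**Step 1: unrecognised pregnancies present at a visit.** The formula is n × (1 − (1 − r)^(days/365)), with half in the carnosine arm.
- Low: n = 80, r = 1%, 14 days gives 0.031 (carnosine arm 0.015).
- Mid: n = 120, r = 3%, 21 days gives 0.210 (0.105).
- High: n = 160, r = 10%, 28 days gives 1.288 (0.644).

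**Step 2: share a strip would detect.** Only pregnancies older than D can be found, so the share is s × (w − D)/w, or 0 where D ≥ w. Each range is for s = 0.90 to 0.99.

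| w (weeks) | D = 1.5 | D = 2 | D = 2.5 |
|---|---|---|---|
| 2 | 22.5–24.8% | 0 | 0 |
| 3 | 45.0–49.5% | 30.0–33.0% | 15.0–16.5% |
| 4 | 56.3–61.9% | 45.0–49.5% | 33.8–37.1% |

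**Step 3: number detected in the carnosine arm per test visit.**
- Low: 0.015 × 0 = 0.
- Mid (w = 3, D = 2): 0.105 × 0.30 to 0.105 × 0.33, about 0.03.
- High: 0.644 × 0.619 = 0.40.

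The range at Visit 3 is similar, before attrition.

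**Step 4: exposure a strip at Visit 2 would avoid.** For a pregnancy detectable that day, the time left until recognition runs from 0 to w − D and averages (w − D)/2.
- w = 3, D = 2: half a week, 3.5 × 2 g = 7 g.
- w = 4, D = 2: one week, 7 × 2 g = 14 g.

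If the pregnancy stayed unrecognised until Visit 3, exposure would be 35 × 2 = 70 g to 49 × 2 = 98 g, but that lies outside the assumed 2–4 week window.

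**Step 5: supply at Visit 3.** Of the 56 days issued, 56 − 49 = 7 to 56 − 35 = 21 days remain (28–84 capsules, 14–42 g). A further 28 days (56 g) would then be issued.

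**Step 6: cost to the trial.** The most a Visit 2 strip would remove across both arms is 1.288 × 0.619 = 0.80 participants, against a planned attrition allowance of 400 − 240 = 160.

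**The case against.** **A test may already be required elsewhere.** The Manual of Operations, consent form, Appendix C and Figures 3–7 were not available to this review. This stands, and the recommendation is conditional on it.

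**The benefit is small.** The mid case is about 0.03 detections in the carnosine arm per test. Section 14 describes the product as generally recognised as safe under good manufacturing practice. The first part stands. The second is a general statement, and section 10 makes a specific exception for pregnancy.

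**The cost is more than the strip.** Section 13 describes the endpoint tests as research-only. A pregnancy test is diagnostic, so it needs a definition of who is tested, private disclosure and a referral route. This stands and is included in the fix.

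Four stronger readings are tempting, and the documents do not support them.
- *The protocol contradicts itself or has no pregnancy check.* It has checks that can catch a known pregnancy. Prescreening review of health information is not purely self-report. The gap is in detecting an unrecognised pregnancy.
- *A strip would find most unrecognised pregnancies.* No document gives a detection share. In the grid above it exceeds half only at w = 4 with D = 1.5. Recognition later than four weeks would raise it. But counting all pregnancies exposed over the 12-week course, with D = 2, recognition at 4 weeks and perfect sensitivity, strips at both visits catch (2 + 2)/(4 + 12) = 25%.
- *A strip would avert 28–56 g, or 70–98 g.* The first range (14–28 days at 2 g) is the total for a conception on the day of Visit 2, which a strip would miss. The second needs non-recognition until Visit 3.
- *Carnosine is known to harm a pregnancy.* The stated reason is missing information, not known harm.

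**Conclusion.** The point holds as a gap in detection. The available text lists no pregnancy test, and none of its listed checks can reveal a pregnancy the participant is unaware of, although the sponsor treats pregnancy as a reason not to give the product.

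A strip at Visits 2 and 3 would detect some of these pregnancies: about 0–62% of those present on the day, or 0–0.4 in the carnosine arm per test visit. Avoidable exposure averages about 7–14 g under mid assumptions. Apart from the dose, the visit timing and the 400 randomised, every input is an assumption, so these figures show scale and are not estimates.

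No endpoint or error rate is affected. A pregnancy present at Visit 2 predates the first capsule, so allocation cannot have caused it, and removing such a participant under blinding should not bias the comparison. This is an optional, low-cost safety improvement.

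**What to change.** Unless one of the unavailable documents already requires it, add a row to the section 12 schedule and to Table 3: a urine pregnancy strip for women who could be pregnant. Define who is tested. Run it on urine already collected, before the first capsule at Visit 2 and before re-supply at Visit 3.

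- **Positive at Visit 2:** give no capsules. Record her as discontinued after randomisation and before first dose, under the loss-of-eligibility criterion in section 9. Say explicitly that she is not a screen failure, because the adjacent definition, "Candidate withdraws and does not complete Baseline Assessment (Visit # 2", could be misapplied to her.
- **Positive at Visit 3:** withhold re-supply, collect unused capsules and discontinue as section 10 states.
- **Both:** keep allocation blinded, tell her privately and refer her for care. Present the reason and date of discontinuation, as section 15 already plans; showing them by arm would be an addition.

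**Cost.** Two strips per eligible woman, one schedule row, one sentence on classification, a consent line on testing and disclosure, and a referral route. No new sample or visit is needed, and the strip can be read during the 20-minute arterial stiffness exam (Table 4).

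**Downsides.** Each positive at Visit 2 is a post-randomisation loss before first dose. Very early pregnancies, and any conceived after Visit 3, would still be missed.

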11. STUDY SUPPLEMENTS

Eligible participants identified from Screening (Visit # 1) will be randomized into carnosine or placebo groups by 1:1 distribution.

Supplement Quality Control and Regulations

As per the Office of Inspector General of the Department of Health and Human Services' report on "Dietary Supplement Labels: Key Elements" – "The Dietary Supplement Health and Education Act of 1994 (DSHEA)"⁴⁴ defines the term "dietary supplement" to mean a product (other than tobacco) intended to supplement the diet that bears or contains one or more of the following dietary ingredients: a vitamin, a mineral, an herb or other botanical, an amino acid, a dietary substance for use by man to supplement the diet by increasing the total dietary intake, or a concentrate, metabolite, constituent, extract, or combination of any of the aforementioned ingredients".^{44, 45}

The United States Food and Drug Administration (US FDA) guidelines specify that merchants selling dietary supplements in the United States are required to follow current good manufacturing practices and their manufacturing plants are required to be inspected by the FDA for "quality of the dietary supplement and to ensure that the dietary supplement is packaged and labeled as specified in the master manufacturing record".⁴⁵ Dietary supplements are not regulated by the FDA for their efficacy but will be inspected for quality, safety, and accuracy.^{44, 45}

Both, Carnosine and placebo, supplements will be prepared by the University of Colorado, Skaggs School of Pharmacy and Pharmaceutical Sciences. Commercially available L-carnosine powder and cornstarch (placebo) will be packaged into gelatin coated capsules in laboratory facilities associated with the state licensed pharmacy of the University of Colorado, Skaggs School of Pharmacy and Pharmaceutical Sciences.

Supplement Capsule Preparation

The following activities and documentations will be performed and saved by the University of Colorado, Skaggs School of Pharmacy and Pharmaceutical Sciences for the Carnosine supplement:

1. Prepare, label, package, and deliver carnosine supplement and chain of custody form to courier as appropriate,
2. Maintain Carnosine chain of custody forms, certificate of analysis forms, and accountability logs (so that clinical / recruitment staff does not have access).
3. Keep completed chain of custody forms, on site for study files and quality assurance purposes.

Placebo Supplement

Placebo supplements will be composed of cornstarch, and will match the composition routinely used in clinical interventional studies. The placebo supplement will also be manufactured by the University of Colorado, Skaggs School of Pharmacy and Pharmaceutical Sciences.

Two hundred participants will receive placebo supplement. Placebo supplement will be available in forms of oral capsules coated with bovine bone derived gelatin. Each capsule will contain 0.5 grams of cornstarch. The participants of the placebo group will be required to take a total of 2 grams of daily cornstarch. Participants will be required to take cornstarch twice per day: 1) Morning – 2 capsules, each containing 0.5 grams of cornstarch and 2) Evening – 2 capsules, each containing 0.5 grams of cornstarch. As per manufacturer instructions, the capsules can be taken with water or any other non-alcoholic drink. There is no pre-requisite of consuming a meal prior to taking the supplement.

The following activities and documentations will be performed and saved by the University of Colorado, Skaggs School of Pharmacy and Pharmaceutical Sciences for the placebo (cornstarch) supplement:

1. Prepare, label, package, and deliver placebo (cornstarch) supplement and chain of custody form to courier as appropriate,
2. Maintain placebo (cornstarch) chain of custody forms, certificate of analysis forms, and accountability logs (so that clinical / recruitment staff does not have access).
3. Keep completed chain of custody forms, on site for study files and quality assurance purposes.

Randomization and Blinding

Blinding of the study personnel recruiting the participants and giving the pill-boxes will be facilitated by the fact that all study participants (Carnosine and placebo) will receive a dietary supplement. All study dietary supplements will be matched in color, consistency, and taste. The primary and secondary endpoints of the study will be determined by core laboratories whose personnel are blinded to supplementation assignment. In addition, the study recruitment and regulatory teams will take steps to ensure that endpoint and adverse event assessments are carried out in a blinded fashion.

Should unblinding occur, the Executive Committee consisting of the study PI, the study physician, and UofL CTU will be informed about the circumstances and they will discuss the circumstances related to the unblinding and further course of action. Any instance of unblinding will be documented in the study database and will be reported to the IRB as required.

Study Supplement Requirements

Study Supplement Packaging and Labeling

Study supplement packaging and labeling will meet all local and federal requirements. Study supplement (carnosine and placebo) label includes the product number, letter "A" or "B", volume, expiration date and time, storage conditions, and contact name and address. All supplements will be labeled for investigational use only.

Supplement capsules will be pre-sorted into monthly (28 day) pill boxes by the unblinded laboratory personnel at the University of Colorado, Skaggs School of Pharmacy and Pharmaceutical Sciences. Pre-sorted pill boxes will be created for a total of 12 weeks per participant. The University of Colorado, Skaggs School of Pharmacy and Pharmaceutical Sciences personnel will label each box clearly as letter "A" or letter "B", indicating whether the box contains Carnosine or placebo supplement. The study personnel at the University of Louisville involved in recruitment, processing, analysis, or any other direct participant contact will be blinded to whether "A" boxes contain Carnosine or placebo, and similarly whether "B" boxes contain Carnosine or placebo. The University of Colorado, Skaggs School of Pharmacy and Pharmaceutical Sciences personnel will ensure that there is absolute consistency in the contents of each series of labeled boxes. The University of Colorado Skaggs School of Pharmacy and Pharmaceutical Sciences will ensure that the contents of each box are not disclosed to anyone involved with the study (staff, investigator, or participant) and will directly and securely send the randomization key to the Randomization Committee (study physician and UofL CTU).

Study Supplement Storage Requirements

L-Carnosine is tested on arrival to establish its purity and retested about every 6-12 months. L-Carnosine receives a three-year dating each time it passes re-assay. Product is stored at controlled room temperature. A sample of packed capsules will be retained, which will be re-assayed about every six months. Potency and stability testing services will be provided using Nuclear Magnetic Resonance and Liquid Chromatography/Mass Spectrometry in the Medicinal Chemistry Core Facility of the University of Colorado, Skaggs School of Pharmacy and Pharmaceutical Sciences.

United States Pharmacopeia (USP) <795> allows 180 day dating for compounded capsules, with extension of dating with ongoing stability studies. Initial potency and purity are established using Nuclear Magnetic Resonance and Liquid Chromatography/Mass

Spectrometry by [name] in the University of Colorado Skaggs School of Pharmacy, Medicinal Chemistry Core Facility. L-Carnosine (bulk powder) has up to a three-year dating from the last date of analysis. [name] will perform ongoing stability studies to ensure that the doses we prepared remain in date throughout the study. Earlier stability studies support a dating of more than three years for our capsules.

Study supplement must be stored at room temperature from the time of manufacture until the time of giving to the study participant. The participant will be informed of these requirements and instructed to strictly follow them.

Study Supplement Accountability

The study supplements will be stored in the UofL CTU, housed at Healthcare Outpatient Care Center ([name]). Upon receipt of study supplement from manufacturer, UofL CTU will open the shipment and verify shipment inventory, temperature, and condition of the study supplement by completing and signing the chain of custody form and forwarding the document to the unblinded manufacturing personnel. The UofL CTU personnel will also compare blinding letter ("A" or "B"). Records shall be kept of all study supplies received, disposition, and any study supplements not used or left over. Study supplement accountability logs contain unblinded information and should be maintained by the Clinical Trials Unit staff only.

The supplements accountability logs will record use of placebo as well.

[figure not shown]
Under no circumstances will any investigator(s) allow study supplement to be used for any purpose other than that specified by the protocol. The study supplement are only to be used as a dietary supplement only for participants of this study and for their specific study group (Carnosine or placebo) only.

Study Supplement Handling and Disposal

Destruction of unused study supplements will proceed as directed by manufacturer or designee, with appropriate documentation completed and retained by site personnel. All records involving receipt, disposition, administration, return and/or destruction of the study supplement will be made available by the PI (or designee) to the Sponsor or designee upon request.

Taking Pre-Existing Medications

Participants can remain on their current / pre-existing medications that they were taking prior to enrollment. Data on medications added or discontinued during the course of the study will be recorded throughout the study to the 4-12 month safety check.

Other Supplements

Participants may not consume any other dietary protein supplements (e.g. Whey protein drinks, Collagen powder, etc.) during the study period. Since Carnosine is an amino acid that serves as a protein building block for muscles, simultaneous consumption of protein supplement has the potential to interfere with the effects of Carnosine on muscles and body physiology.

